4. METHODS

4.1. Study Plan

For brief explanation of the study plan please go to Figure 1, the study plan.

[figure not shown]

Figure 1. The Study Plan

4.3. Type and Design of Study

This study is an observational study, conducted at the pediatric department at three hospitals in Indonesia. It will recruit hospitalized children aged between 2 months to 5 years who meet the inclusion and exclusion criteria. Participants will be followed up for maximum 13 days' hospitalization. At day 14th after hospitalization date each participant will be assessed for his/her symptoms, clinical data, clinical outcome, and serum specimen collection. The end of their participation will be ended on day 30th after hospitalization date, after followed up phone from RA.

Laboratory test procedures will be conducted during the study and/or after study completion. Chest X-Ray, CBC, blood and respiratory specimen cultures including antibiotic resistance test will be performed either as part of standard of care or study addition. Rapid tests for Influenza A and B; Respiratory Syncytial Virus (RSV); and Legionella will be performed as study requirement. C-reactive protein (CRP) and Procalcitonin (PCT) will also be measured for study interest. Molecular assays to identify bacterial and viral pathogens and serological assays to detect infections of several viruses and bacteria will be conducted at the reference laboratory. Any left-over respiratory specimens and/or plasma from day 2 and 3 hospitalization will be stored for archiving.

Specimen that will be stored for archiving, will be maintained for further laboratory testing for up to 5 years after the study is completed. After 5 years, with the decision of Steering

Committee and Governing Board, specimens in the INA-RESPOND specimen repository in NIH RD Jakarta, will either be destroyed, or after IRB approval, transferred to another existing protocol or a repository.

4.4. Population and Sample Size

This is a preliminary study to characterize the pathogens present in this cohort. The number of participants' that will be enrolled is based on the number of pneumonia cases in 5 years old children or less. This study plan to enroll with total of 275 participants.

With 275 participants, the 95% confidence interval for the prevalence of each pathogen will be no greater than $\pm 7\%$. The study is not powered to test the diagnostic accuracy of the algorithm. The algorithm developed from this study will be evaluated in a larger study, powered to estimate sensitivity and specificity. As a result, no formal power calculations have been provided.

4.5. Eligibility Criteria

4.5.1. Inclusion criteria

- Pediatric inpatients whose ages range from 2 months to 5 years.
- Meet the case definition for pneumonia which is cough or fever with at least one other following symptoms:
 - ✓ Shortness of breath, marked by at least one of the following signs: head bobbing; nasal flaring; chest indrawing or intercostal retracting.
 - ✓ Tachypnea (RR ≥ 40 /minute, for children 1 to 5 years old, and RR ≥ 50 /minute, for children 2 to 12 months old)
 - ✓ Grunting
 - ✓ Crackles/rhonchi
 - ✓ Decreased vesicular breath sound
 - ✓ Bronchial breath sound
 - ✓ Chest x-ray consistent with pneumonia
- Comply with all study procedures including to store required specimens for diagnostic testing and archiving.

4.5.2. Exclusion criteria

- Being hospitalized for more than 24 hours at enrollment
- Having a cancer or history of cancer
- Having a history of long term exposed of steroid (at the minimum of 2 months)
- Having any condition that might interfere with study procedure and compliance (based on clinicians' judgement).

4.6. Study Procedures and Evaluations

4.6.1. Screening and enrollment

Potential pediatric participants who come to the emergency room or outpatient clinic and have been admitted to the hospital will be referred by physicians at participating hospitals to be observed and screened according to the study eligibility criteria. If the patients meet the criteria, the parent/legal guardian will be offered information about the study. If agree, he/she must provide a documented informed consent form (ICF) and will undergo the enrollment procedures. Participants who have finished or completed the study can't be re-screened and re-enrolled into the study.

4.6.2. Baseline (study visit day 0 = day 1 hospitalization)

Following baseline procedures will be collected on all participants, these include:

1. Demographic data including age, sex, birth order, parent's education, parent's occupation, and family income.
2. Medical history including history of mother's pregnancy and breastfeeding, vaccination, vitamin A supplementation, growth and development, history of past and presence illness including congenital disease, and allergic.
3. Clinical data including chief complaint, sign and symptoms, vital signs, anthropometric, initial diagnosed, comorbidities, chest X-Ray (if available).
4. Treatment including antibiotic, steroid, and oxygen therapy.
5. Risk factors including smoking exposure, TB contact, poultry contact (contact with sick and/or dead poultry and contact with poultry's faeces

and/or derivative), contact with someone who has cold, air pollution exposure, going to daycare, living in a densely populated area.

6. Laboratory examinations including CBC test, CRP, PCT, Blood gas analysis, blood culture, respiratory culture (if available), antimicrobial sensitivity test, HIV test, influenza rapid test, legionella Ag, Gram negative test, AFB, Xpert MTB/RIF (according to SoC).
7. Laboratory examinations at the reference laboratory including molecular and serological tests.
8. Specimen archiving including left over specimens (whole blood, serum, urine, NPS, sputum/induced sputum) and isolate from culture (if available)

Whole blood and serum must be collected and processed during 24 hours after the enrollment. Other specimens' collection can be postponed up to 48 hours after the enrollment.

Blood culture should be performed on all participants prior to antibiotic administration in the study site, however any condition where blood culture is done after the antibiotic administer is still allowed. Blood culture worked prior to the enrollment will be recorded in the CRF and no repetition needed.

For the detail of study procedures, please check out the Manual of Procedures (MoP).

4.6.3. Follow up during hospitalization (Daily study visit day 1 up to day 12 = day 2nd up to day 13th hospitalization)

This follow up schedule will be conducted daily during hospitalization of participants, but limited up to daily study visit day 12 (day 13th hospitalization). The following procedures will be collected from each participant, if available:

1. Clinical data including sign and symptoms, vital signs, and chest X-Ray.
2. On-going treatment
3. Specimen archiving. Any respiratory left-over specimen and/or plasma from daily study visit day 1 & 2 (day 2 & 3 of hospitalization) will also be collected to be stored.

4.6.4. During discharge

Hospitalization and discharge information including complication, discharge diagnoses, and clinical outcome. Procedure will be collected at discharge day.

3.6.5. Follow up (Study Visit Day 14th after hospitalization)

This study follow up will be conducted at day 14th after hospitalization. There will be \pm 4-days window period for this follow up schedule. The following procedures will be collected from each participant, if available:

1. Clinical data including sign and symptoms, vital signs, anthropometric, clinical outcome.
2. Laboratory examinations at the reference laboratory including serological tests.
3. Specimen archiving. Serum will be collected and stored.

3.6.6. Follow up (day 30th after hospitalization)

In this follow up schedule, the RA will conduct follow up by phone and the participants will be assessed for their self-reported health condition. If needed, home visit can be conducted for this visit. There will be \pm 4-days window period for this follow up schedule. No specimen will be collected in this follow up.

3.6.7. Laboratory procedures for Molecular and Serological Testing

This study will carry out molecular and serological testing that will be done at the reference laboratory. The study will cover all the costs of those tests.

Table 1 and Table 2 will furtherly explain the required specimen volume and tests needed. Also see appendix A for the work flow.

Table 1. The research specimen and laboratory testing

Visit /Time	Collected Specimen	Amount	Laboratory Testing at	
			Hospital	Reference Lab
Enrollment (up to 24 hours after enrollment)	Whole Blood	2 x 1 ml – 2 ml blood 1 x 3 ml blood	Blood culture (2 sides) CBC	PCR (Streptococcus pneumonia, Staphylococcus aureus, Haemophilus influenza)
	Serum	1 x 4 ml blood	CRP, Procalcitonin, HIV (can be done up to 5 days after enrollment)	Serology IgM and IgG (Influenza A, B, RSV, Parainfluenza virus, Adenovirus, Mycoplasma pneumonia, Chlamydia pneumonia, Bordetella pertussis, Legionella pneumonia)
Enrollment (up to 48 hours after enrollment)	Urine	1 ml – 3 ml urine	Rapid test Legionella antigen	PCR (Legionella pneumoniae, Leptospira)
	Nasopharyngeal swab	2 VTM (1.5 ml)	Rapid test Influenza Rapid test RSV	PCR (18- Viral Panel)
	Sputum/induced sputum	2 ml	Culture, MTB (genexpert, if AFB positive)	PCR (11 Bacterial and 18 viral panel)
	Other resp specimen (leftover – effusi pleura, BAL)	If available	Culture, MTB (genexpert, if AFB positive)	PCR (11 Bacterial and 18 viral panel)
Daily study visit during hospitalization	Left-over respiratory specimen and/or plasma (Daily study visit day 1 & 2 (day 2 & 3 of hospitalization)	If available	None	TBD
Study Visit Day 14th after hospitalization	Serum	4 ml blood	None	Serology IgM and IgG (Influenza A, B, RSV, Parainfluenza virus, Adenovirus, Mycoplasma pneumonia, Chlamydia pneumonia, Bordetella pertussis, Legionella pneumonia)
Follow-up Day 30 th after hospitalization	None	None	None	None

NOTE: Maximum amount of blood drawn in pediatric patients weight 7.3 – 45.5 kgs is 10 ml - 30 ml at any one time or 60 ml – 350 ml cumulative during hospitalization or maximum 1 month (Garza D, Becan-McBride K).

Table 2. PCR Panel for Bacterial & Viral Pathogens

PCR Viral Panel	PCR Bacterial Panel
Human Influenza A virus	Haemophilus influenza
Human Influenza B virus	Streptococcus pneumoniae
Adenovirus	Legionella pneumoniae
Enterovirus	Mycoplasma pneumoniae
Respiratory Syncytial Virus A	Chlamydia pneumoniae
Respiratory Syncytial Virus B	Chlamydia psittaci
Human Metapneumo virus	Bordetella pertussis
Rhinovirus	Moraxella catarrhalis
Human Parainfluenza Virus 1	Staphylococcus aureus
Human Parainfluenza Virus 2	Klebsiella pneumoniae
Human Parainfluenza Virus 3	Burkholderia pseudomallei
Human Parainfluenza Virus 4	
Corona Virus 22E	
Corona Virus OC43	
Corona Virus SARS	
Corona Virus NL63	
Parechovirus	
Bocavirus	

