3.2. Secondary Objectives

- To identify the etiologies of pneumonia in children in Indonesia, which are currently unavailable.
- To document outcomes in pediatric patients with pneumonia in Indonesia.
- To evaluate the performance of each rapid point of care test (to detect influenza and viral syncytial viruses, legionella urinary antigen, biomarkers of bacterial infections (CRP and PCT), and standard of care procedures (Chest X-ray, O₂ saturation, CBC, blood Gas Analyses (if available) compared to the gold standard molecular assays in differentiating virus and bacterial infections.
- To analyze the performance of combined tests in differentiating virus and bacterial infections.
- To provide information regarding updated strains of circulating respiratory viruses and pathogens in children.

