Appendix D: Guidelines for maximum blood draw for pediatric patients

Patient's Weight Pounds	Patient's Weight Kilograms (approx.)	Maximum Amount to be drawn at any one time (mL)	Maximum Amount of blood—cumulative to be drawn during a given hospital stay (1 month or less-mL)
6-8	2.7-3.6	2.5	23
8-10	3.6-4.5	3.5	30
10-15	4.5-6.8	5	40
16-20	7.3-9.1	10	60
21-25	9.5-11.4	10	70
26-30	11.8-13.6	10	80
31-35	14.1-15.9	10	100
36-40	16.4-18.2	10	130
41-45	18.6-20.5	20	140
46-50	20.9-22.7	20	160
51-55	23.2-25.0	20	180
56-60	25.5-27.3	20	200
61-65	27.7-29.5	25	220
66-70	30.0-31.8	30	240
71-75	32.3-34.1	30	250
76-80	34.5-36.4	30	270
81-85	36.8-38.6	30	290
86-90	39.1-40.9	30	310
91-95	41.4-43.2	30	330
96-100	43.6-45.5	30	350

Reference: Becan-McBride, K., Phlebotomy Handbook - Blood Collection Essentials, Seventh Edition

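### The fixed 4 mL serum draw in Table 1 exceeds the protocol's own Appendix D single-draw limit below 4.5 kg, and the Table 1 note gives no limit below 7.3 kg

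*Combined protocol and SAP*

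**What the plan says.** Section 3.6.7 introduces the specimen tables with the words "Table 1 and Table 2 will furtherly explain the required specimen volume and tests needed". For whole blood at enrolment, Table 1 lists "2 x 1 ml – 2 ml blood 1 x 3 ml blood": two culture samples of 1-2 mL and one 3 mL sample. For serum it lists one 4 mL blood sample at enrolment and another 4 mL at day 14. None of these volumes varies with weight.

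The note under Table 1 says "Maximum amount of blood drawn in pediatric patients weight 7.3 – 45.5 kgs is 10 ml - 30 ml at any one time", and cites a phlebotomy textbook rather than Appendix D.

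Appendix D prints the full table of limits. Its column headed "Maximum Amount to be drawn at any one time (mL") includes three rows that the note leaves out: 2.5 mL for 2.7-3.6 kg, 3.5 mL for 3.6-4.5 kg and 5 mL for 4.5-6.8 kg.

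On timing, section 4.6.2 says "Whole blood and serum must be collected and processed during 24 hours after the enrollment". It also says of culture that "Blood culture worked prior to the enrollment will be recorded in the CRF and no repetition needed". Day 14 procedures are done where available (section 3.6.5). Section 4.5.1 admits children from 2 months of age and sets no minimum weight. Section 10.6 explains that the age floor was chosen because of blood volume.

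**The concern.** Two parts of the same protocol give different answers for the smallest infants. A site that follows Table 1 and its note can take 4 mL at once from a child below 4.5 kg. That is more than Appendix D allows, and nothing at the point of use warns the site. In the supplied text, Appendix D appears only in the contents list and as the appendix itself. No supplied sentence says that it governs Table 1.

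The protocol rests its minimal-risk claim on the blood draw being the only study intervention (section 10.8), so this is the procedure whose limits should be unambiguous. At day 14, Table 1 lists no hospital test for the serum. It goes to the reference laboratory and to storage, so no bedside need is stated that would justify going over the limit.

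There is also a smaller data issue. The enrolment serum supplies CRP and PCT, two of the tests under evaluation (section 3.2). Without a common rule, sites may stage, shorten or skip draws in small infants in different ways.

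**Working it through.** **Inputs.** Volumes come from Table 1: cultures 2 × 1-2 mL, whole blood 3 mL, serum 4 mL at enrolment and 4 mL at day 14. Limits come from Appendix D.

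**1. Reproduce the note.** Across the Appendix D rows from 7.3 to 45.5 kg, the smallest and largest single-draw limits are 10 and 30 mL, and the cumulative limits are 60 and 350 mL. These are the note's figures exactly. The note therefore summarises 17 of the 20 rows and omits the three below 7.3 kg. With all rows it would read 2.7-45.5 kg, 2.5-30 mL at one time, 23-350 mL cumulative.

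**2. Enrolment set.** Low: 2×1 + 3 + 4 = 9 mL. High: 2×2 + 3 + 4 = 11 mL. With culture already done: 3 + 4 = 7 mL.

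**3. Each sample, and the whole set, against the single-draw limit** (ratio = volume / limit).

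| Weight (kg) | Limit (mL) | Serum, 4 mL | Whole blood, 3 mL | One culture, at most 2 mL | Whole set at one time, 9-11 mL |
|---|---|---|---|---|---|
| 2.7-3.6 | 2.5 | over by 1.5 (1.60) | over by 0.5 (1.20) | within (0.80) | 3.6-4.4 |
| 3.6-4.5 | 3.5 | over by 0.5 (1.14) | within (0.86) | within (0.57) | 2.6-3.1 |
| 4.5-6.8 | 5 | within (0.80) | within (0.60) | within (0.40) | 1.8-2.2 |
| 7.3-18.2 (five rows) | 10 | within (0.40) | within (0.30) | within (0.20) | 0.9-1.1 |

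The serum and whole-blood columns need no assumption about grouping: each is a single Table 1 sample taken as listed. The last column applies only if the whole set is drawn at one time. With culture already done, the set is 7/5 = 1.4 times the limit at 4.5-6.8 kg and 7/10 = 0.7 times at 7.3-18.2 kg.

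**4. Can draws be staged?** At enrolment, yes, within the 24-hour window. Serum as 2 + 2 mL and whole blood as 1.5 + 1.5 mL each fit even the 2.5 mL row. Day 14 is one visit with no such provision.

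**5. Cumulative volume, study tubes only.** 9 + 4 = 13 mL to 11 + 4 = 15 mL (7 + 4 = 11 mL with culture already done). The lowest cumulative limit is 23 mL, so study tubes alone stay under it. Blood taken for routine care is not in this sum.

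**The case against.** The strongest reply is that the limits are in the protocol. Appendix D prints every low-weight row, it restricts blood drawn at one time, and the 24-hour window lets a site split the enrolment tubes. Procedural detail is left to the Manual of Procedures (section 4.6.2), which may hold a weight rule. Clinicians may exclude a child on judgement (section 4.5.2) or withdraw one for safety (section 4.7). The age floor already addresses blood volume, and the excess is at most 1.5 mL.

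Much of this stands, and it rules out some stronger readings:

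- A reader might infer that a site obeying Appendix D must cut the enrolment volumes. It need not, because it can stage them.
- A reader might infer that the blood culture is at risk, given that "Blood culture should be performed on all participants prior to antibiotic administration in the study site". Each culture sample is 1-2 mL and fits every row on its own. Culture is touched only if all tubes are taken together.
- A reader might infer that the enrolment set breaks the limits for most children. That depends on taking it at one time. Even then, at 7.3-18.2 kg the 9 mL set fits and the 11 mL set does not.

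The reply does not remove the printed conflict. Table 1 gives serum as one 4 mL sample and calls its volumes required. The safeguards cited set no volume by weight, and an age floor does not limit weight. Day 14 has no staging window.

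**Conclusion.** The point holds for children below 4.5 kg and should be fixed. As printed, the 4 mL serum draw exceeds the Appendix D single-draw limit by 0.5 mL at 3.6-4.5 kg and by 1.5 mL at 2.7-3.6 kg, at both visits. The 3 mL whole-blood sample exceeds it by 0.5 mL at 2.7-3.6 kg. Exactly 4.5 kg falls in two rows (3.5 and 5 mL), so the breach is clear only below that weight.

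Conditionally, if the whole enrolment set is taken at one time, it also exceeds the 5 mL limit at 4.5-6.8 kg, and an 11 mL set exceeds the 10 mL limit at 7.3-18.2 kg.

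Confidence is high for the mismatch between Table 1 and Appendix D. It does not extend to practice. The documents give no weights, so they do not show how many children below 4.5 kg would enrol, or that any would be overdrawn. The Manual of Procedures is not among them. The cumulative finding covers study tubes only.

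**What to change.** Amend the Table 1 note in three ways.

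1. Extend it to all Appendix D rows: from 2.7 kg, 2.5-30 mL at one time and 23-350 mL cumulative, with a reference to Appendix D.
2. State that the Appendix D single-draw limit overrides the Table 1 volumes at every weight and visit.
3. Say how to comply. At enrolment, stage the draws within the 24-hour window or reduce them. At day 14, cap the serum draw at 3.5 mL from 3.6 to below 4.5 kg, and at 2.5 mL below 3.6 kg.

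Any priority order among tubes should be left to the study team, because the documents give no minimum assay volumes. If the Manual of Procedures already holds these rules, citing it in the note is enough.

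The cost is a short protocol amendment. The downside is an extra needle stick or less serum in the smallest infants. At day 14 the caps remove 0.5 of 4 mL (12.5%) or 1.5 of 4 mL (37.5%), so some reference-laboratory serology or archiving may be lost for those children.

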4.7. Study Withdrawal

Participants may voluntarily withdraw from the study for any reason at any time. The Investigator also may withdraw participants from the study in order to protect their safety and/or if they are unwilling or unable to comply with required study procedures after consultation with the Research Team.

Participants also may be withdrawn if the study sponsor, government or regulatory authorities, or Institutional Review Board (IRB) terminate the study prior to its planned end date. Every reasonable effort will be made to complete a final evaluation of participants who terminate from the study prior to the planned termination time period, and study site team will record the reason(s) for all withdrawals from the study in participants' study records.

4.8. Study disposition status

Study disposition status will be completed by the Research Assistant when the participants considered as end of study. Participants followed until 30 days after hospitalization will be considered as completing the study procedure and end of study.

The rest of the Participants will be considered as end of study at the following time point:

- Participant is dead
- Participant withdraws consent
- Participant who can't be reached for follow-up visit (lost to follow-up)
- Based on investigator discretion
- Termination of study

4.9. Study Instruments

The following instruments will be used in this study. Further information will be found in the study MOP.

a. Forms

- Informed consent
- Source Document Worksheet (SDW)
- Case Report Form (CRF)

b. Log

- Screening log
- Enrollment log
- Specimen log

c. Electronic Database

- OpenClinica
- Manual Specimen Repository Database
- INA-RESPOND Electronic Data Management System (EDMS)

5. LABORATORY SPECIMENS AND BIOHAZARD CONTAINMENT

5.1. Universal Precaution and Biohazard Containment

As the transmission of blood-borne pathogens and air-borne pathogens can occur through contact with contaminated needles, blood, respiratory specimens and its products, appropriate blood and secretion precautions will be employed by all personnel

in the drawing of blood, collecting respiratory specimen, shipping and handling of all specimens for this study. These will be further described in the study MoP.5.2 Specimen Collection and Aliquots

Each study site will adhere to standards of good clinical laboratory practice and the study SOPs for specimen management including proper collection, processing, aliquoting, labeling, transport, and storage of specimens. In general, all laboratory procedures will be done locally in the study sites and in the reference laboratory for molecular and serological testing. These will be further described in the study MoP.

Samples will be collected at baseline and some follow-up visits according to the study procedures. If available, specimens will be tested either on hospital laboratory or reference laboratory. Samples will be coded with a unique identifier that does not contain any information capable of linking the sample to the participant. A code that links the unique identifier with the study volunteer will be kept in a locked file cabinet in a secure room or on a password-protected computer. Only authorized personnel will have access to the code.

Specimens from blood approximately will be divided into aliquot of 3. One will be stored at the site and two will be sent to the reference laboratory.

